---

## Table of Abbreviations

In addition to the study glossaries and abbreviations defined in the protocol, here is a table of abbreviations used in this document:

Abbreviation/Acronym	Definition
ADaM	Analysis Data Model data sets
BDSG	Biomedical Data Stewardship Governance
CRF	Case Report Form
IPCW	Inverse Probability Censoring Weighting
IPD	Important Protocol Deviation
ITT	Intent to Treat
SAP	Statistical Analysis Plan
SDTM	Study Data Tabulation Model data sets
SOA	Schedule of Assessments
TFL	Table, Figure, Listing

## 1. Introduction

The purpose of this statistical analysis plan (SAP) is to provide details of the statistical analyses that have been outlined within the protocol amendment 3 for the Talimogene Laherparepvec, Study 20110266 dated 23 March 2018. The scope of this plan includes the three interim analyses, the primary analysis, the final analysis, and one additional ad hoc analysis that may also be conducted before the planned primary and/or final analysis if interim data are required for submission to regulatory authorities. These analyses will be executed by the biostatistics department unless otherwise specified.

This study will have data collected and analyzed in Amgen-owned databases and systems and will adhere to approved Data Element Standards and International Case Report Form (CRF) Standards, if available, established by Biomedical Data Stewardship Governance (BDSG). Amgen-owned databases and systems include vendor and service provider databases built for Amgen-only use.

## 2. Objectives

### 2.1 Primary

To estimate the treatment effect of neoadjuvant talimogene laherparepvec plus surgery compared to surgery alone on recurrence-free survival (RFS).

### 2.2 Secondary

The secondary objectives are:

- To estimate the effect of neoadjuvant talimogene laherparepvec plus surgery compared to surgery alone on landmark RFS by year
- To estimate the effect of neoadjuvant talimogene laherparepvec plus surgery compared to surgery alone on rate of histopathological tumor-free margin (R0) surgical resection
- To estimate the effect of neoadjuvant talimogene laherparepvec on rate of pathological complete response (pCR) (Arm 1 only)

- To estimate the effect of neoadjuvant talimogene laherparepvec plus surgery compared to surgery alone on local recurrence-free survival (LRFS), regional recurrence-free survival (RRFS) and distant metastases-free survival (DMFS)
- To estimate the effect of neoadjuvant talimogene laherparepvec plus surgery compared to surgery alone on landmark overall survival (OS) by year, and overall survival (OS)
- To estimate response to neoadjuvant talimogene laherparepvec overall and separately in injected and uninjected lesions during treatment (Arm 1 only)
- To evaluate the safety of neoadjuvant talimogene laherparepvec plus surgery compared to surgery alone

### **2.3 Exploratory**

The exploratory objectives are:

- To explore the correlation between baseline intratumoral CD8+ cell density and clinical outcomes
- To explore the correlation between changes in an intratumoral CD8+ cell density during talimogene laherparepvec treatment and clinical outcomes
- To investigate the correlation between the changes in the population of tumor-specific cytotoxic T-cells during treatment and clinical outcomes
- To assess blood and tumor for potential biomarkers which correlate with or predict clinical outcomes to talimogene laherparepvec

## **3. Study Overview**

### **3.1 Study Design**

This is a phase 2, multicenter, randomized, open-label study to estimate the efficacy of talimogene laherparepvec as a neoadjuvant treatment followed by surgery compared to surgery alone in subjects with resectable stage IIIB, IIIC, or IVM1a melanoma.

Approximately 150 subjects with completely resectable melanoma and at least one injectable lesion will be randomized 1:1 to receive the following:

- Arm 1: Talimogene laherparepvec for 6 doses followed by surgical resection of melanoma tumor lesion(s).
  - Talimogene Laherparepvec:

Talimogene laherparepvec will be administered by intralesional injection into the injectable cutaneous, subcutaneous, and nodal tumors initially at a dose of  $10^6$  plaque forming units (PFU)/mL at day 1 of week 1 followed by a dose of  $10^8$  PFU/mL at day 1 ( $\pm$  3 days) of weeks 4, 6, 8, 10 and 12 or until all injectable tumors have disappeared, or intolerance of study treatment, whichever occurs first. Due to the mechanism of action of talimogene laherparepvec, subjects may experience transient growth in existing tumors or the appearance of new tumors prior to maximal clinical benefit of talimogene laherparepvec. Subjects who experience growth in existing tumors

or the appearance of new tumors will be allowed to remain on talimogene laherparepvec treatment until week 12 of therapy unless, in the opinion of the investigator, immediate surgical resection or any other treatment for melanoma is warranted. If talimogene laherparepvec treatment will end prior to week 12, the investigator or designee should notify the sponsor's medical monitor as soon as possible.

- Surgical Resection of Melanoma Tumor Lesions(s):

For subjects who complete 12 weeks of talimogene laherparepvec treatment, surgical resection of melanoma lesion(s) will be performed at any time during weeks 13 to 18. Subjects who stop talimogene laherparepvec prior to week 12 due to disappearance of all injectable tumor lesions, intolerance to talimogene laherparepvec, or any other reason will undergo adequate surgical resection of melanoma lesion(s) or tissue where melanoma was present before achieving CR, within 1 to 6 weeks after the last dose of talimogene laherparepvec. If surgery will be performed prior to week 12, the investigator or designee should notify the sponsor's medical monitor as soon as possible. Refer to protocol Appendix F for surgery guidelines.

- Arm 2: Immediate surgical resection of melanoma tumor lesion(s)
  - Surgical resection of melanoma tumor lesion(s) will be performed after enrollment any time during weeks 1 to 6.

Randomization will be stratified by disease stage (IIIB nodal versus IIIB in-transit versus IIIC nodal versus IIIC in-transit with nodal versus IVM1a) and planned adjuvant therapy (adjuvant systemic therapy [eg, INF $\alpha$ , ipilimumab] with or without radiotherapy versus radiotherapy without adjuvant systemic therapy versus none). Following surgery, adjuvant systemic therapy and/or radiotherapy may be administered at the investigator's discretion and per the institutional standard of care. Subjects will be followed for safety approximately 30 (+ 15) days after surgery and for disease recurrence (local, regional, or distant), subsequent anticancer therapy for melanoma, adverse events thought to be potentially related to talimogene laherparepvec (Arm 1 only), and survival every 3 months ( $\pm$  30 days) for first 3 years after the end of the safety follow-up period and then every 6 months ( $\pm$  30 days) until death, subject withdraws full consent, or up to 5 years after the last subject is randomized, whichever is first. Thereafter, subjects randomized to Arm 1 who received at least a single dose of talimogene laherparepvec will be followed under an ongoing separate registry protocol (study 20120139) for the long-term survival

follow-up of subjects treated with talimogene laherparepvec. The registry protocol will also monitor for late and long-term adverse events thought to be potentially related to talimogene laherparepvec and use of subsequent anticancer therapy for melanoma. Subjects who, after the long-term follow-up period of this study (Study 20110266), elect to participate in the registry study (Study 20120139) must sign new informed consent form before any registry protocol-specific activities.

### 3.2 Sample Size

All analyses will be descriptive with no formal hypothesis testing. The primary objective of the study is to estimate the treatment effect, as measured by the hazard ratio of RFS, of talimogene laherparepvec neoadjuvant therapy followed by surgery (Arm 1) compared to surgery alone (Arm 2) in subjects with resectable, stage IIIB to IVM1a melanoma. Approximately 150 subjects will be randomized 1:1 to receive Arm 1 vs Arm 2 stratified by: (i) disease stage (IIIB nodal vs IIIB in-transit vs IIIC nodal vs IIIC in-transit with nodal vs IVM1a), and (ii) planned adjuvant therapy (adjuvant systemic therapy [eg, INF $\alpha$ , ipilimumab] with or without radiotherapy vs radiotherapy without adjuvant systemic therapy vs none). Primary efficacy analysis of RFS will be based on the Intent to Treat Analysis Set. An overall between-group difference in RFS will be evaluated with a log-rank test and corresponding proportional hazards model without stratification. The Kaplan-Meier (KM) method will be used to estimate 1-year, 2-year, 3-year, 5-year, and overall RFS. Subjects who are not confirmed to be disease-free post-surgery (i.e., who do not have an R0 surgical outcome) or who withdraw prior to surgery will be considered a failure at randomization for RFS, RRFS, LRFS and DMFS. The primary analysis for the primary endpoint will occur at the later time of either the occurrence of approximately 64 events (local, regional, or distant recurrence of melanoma or death) or approximately 2 years after the end of randomization. An 80% CI will be estimated for the hazard ratio of RFS. In addition, an 80% CI will also be estimated for the between-arm difference (Arm 1 – Arm 2) in 2-year RFS, i.e.,  $\Delta$  2-year RFS. It is assumed that: (i) RFS is exponential over the first 2 years, (ii) the 2-year RFS for Arm 2 is about 0.60 (Eggermont et al, 2008), and that there will be a 10% exponential probability of drop-out by the primary analysis. Simulations were performed for various scenarios from 0.05 to 0.15 to evaluate the following parameters assuming possible true  $\Delta$  2-year RFS values of 0.10, 0.125, and 0.15: (i) the average  $\Delta$  2-year RFS 80% CI and its width, (ii) the probability that the  $\Delta$  2-year RFS 80% CI is above 0, and (iii) the average number of events at the

primary analysis. The possible true  $\Delta$  2-year RFS values were translated to a RFS hazard ratio (HR) (Arm 1 relative to Arm 2) and the HR 80% CI and the probability of it being  $< 1$  were calculated based on the simulated average number of events. The average width of the  $\Delta$  2-year RFS 80% CI was 0.20 (Table 1).

**Table 1. Study Design Characteristics**

2-year RFS			RFS HR	Ave. $\Delta$ 80% CI			Prob. $\Delta$ 80% CI $> 0$	Ave. HR 80% CI		Prob. HR 80% CI $< 1$	Ave. Events
Arm 1	Arm 2	$\Delta$		LL	UL	Width		LL	UL		
0.700		0.100	0.70	0.00	0.20	0.20	0.51	0.51	0.96	0.56	64
0.725	0.60	0.125	0.63	0.02	0.22	0.20	0.62	0.45	0.87	0.71	62
0.750		0.150	0.56	0.05	0.25	0.20	0.74	0.40	0.78	0.83	60

RFS, Recurrence-free Survival; HR, Hazard Ratio; CI, Confidence Interval; LL, Lower Limit; UL, Upper Limit; Ave, Average; Prob., Probability;  $\Delta$  = Arm 1 – Arm 2-year RFS

#### 4. Study Endpoints and Covariates

##### 4.1 Study Endpoints

##### 4.1.1 Primary Endpoint

Recurrence-Free Survival (RFS): The event for RFS is defined as the first of local, regional, or distant recurrence of melanoma or death due to any cause. RFS is defined as time from randomization to the date of the event. The following **four** rules will be used:

1. For subjects having not experienced an event by the cutoff date, RFS will be censored at the last valid tumor evaluation (refer to Section 6 for the definition of last valid tumor evaluation).
2. Subjects who are not confirmed to be disease-free post-surgery (i.e., who do not have an R0 surgical outcome) will be considered to have an event at randomization for RFS.
3. Subjects who withdraw prior to surgery will be considered to have an event at randomization for RFS.
4. Subjects with a non-melanoma tumor or a second malignancy identified before or at surgery will be censored at the day after randomization.

Alternative RFS definitions will be evaluated in sensitivity analyses as follows.

- **RFS Sensitivity # 1: RFS is defined as the first of local, regional, or distant recurrence of melanoma or death due to any cause, regardless of surgical outcome, achieved by omitting rule 2.**

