10. STATISTICAL CONSIDERATIONS

10.1 Study Endpoints, Analysis Sets, and Covariates

10.1.1 Study Endpoints

10.1.1.1 Primary Endpoint

- Recurrence-free Survival (RFS): RFS is defined as time from randomization to the date of the first of local, regional, or distant recurrence of melanoma or death due to any cause.

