10.1.2 Analysis Sets

Intent to Treat Analysis Set

The primary analysis of all efficacy endpoints of the study will be conducted on the intent to treat analysis set defined as all randomized subjects who were randomized to either treatment arm. All subjects will be analyzed according to their treatment randomization.

Safety Analysis Set

The safety analysis set will include all subjects who received talimogene laherparepvec or surgical resection of melanoma tumor lesion(s). The safety analyses will be performed by treatment received.

Efficacy Analysis Set

The efficacy analysis set will include all subjects in Arm 1 who received at least one dose of talimogene laherparepvec and surgical resection of melanoma tumor lesion(s) and all the subjects in Arm 2 who received surgical resection of melanoma tumor lesion(s). In addition, all subjects in the efficacy analysis set must have achieved histopathologic tumor-free margin (R0) status after surgery and should not have any important protocol deviations which may affect the efficacy endpoints. The efficacy analysis set may be used for sensitivity analysis of efficacy endpoints if needed.

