#### 4.1.2.1.2 Other Endpoints

- Landmark RFS by year: The Kaplan-Meier (K-M) estimate of RFS rate at 1 year, 2 years, 3 years, and 5 years
- Rate of histopathology tumor-free margin (R0) surgical resection
- Rate of pathological complete response (pCR) (Arm 1 only)
- Local recurrence-free survival (LRFS): Time from randomization to the earlier date of the first of local disease recurrence or death due to any cause. Local recurrence is defined as histologically or cytologically confirmed reappearance of melanoma in the area of up to 2 cm from the scar from the surgical excision or at the edge of the skin graft if that was used for closure. For subjects not having experienced an event by the cutoff date, LRFS will be censored at the last valid tumor evaluation before the data cutoff date. An event will be imputed at randomization for subjects who do not have an R0 surgical outcome. Subjects with a non-melanoma tumor identified at surgery will be censored at the day after randomization. **Sensitivity analyses as per RFS Sensitivity #1 (see Section 4.1.1) will be performed for LRFS.**
- Regional recurrence-free survival (RRFS): Time from randomization to the date of the first of regional disease recurrence or death due to any cause. Regional recurrence excludes local recurrence and is defined as histologically, cytologically, or radiographically confirmed reappearance of melanoma in the regional lymph node basin. New in-transit melanoma metastases in the regional lymphatic drainage will be reported as regional recurrence. Histological or cytological confirmation of new in-transit metastases is recommended but is not required. For subjects not having experienced an event by the cutoff date, RRFS will be censored at the last valid tumor evaluation before the data cutoff date. Subjects with a non-melanoma tumor identified at surgery will be censored a day after randomization. **Sensitivity analyses as per RFS Sensitivity #1 (see Section 4.1.1) will be performed for RRFS.**

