- Distant metastases free survival (DMFS): Time from randomization to the earlier date of the first of distant metastases or death due to any cause. Distant metastases exclude local and regional recurrence and will include distant cutaneous/subcutaneous metastases, distant nodal metastases, or visceral, central nervous system, brain, or bone metastases. For subjects not having experienced an event by the cutoff date, DMFS will be censored at the last valid tumor evaluation before the data cutoff date. Subjects with a non-melanoma tumor identified at surgery will be censored at the day after randomization. Sensitivity analyses **as per RFS Sensitivity #1 (see Section 4.1.1) will be performed for DMFS.**
- Overall survival (OS): Time from randomization to death due to any cause
- Landmark OS by year: The Kaplan-Meier (K-M) estimate of the overall survival rate at 1 year, 2 years, 3 years and 5 years.

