## 11. Changes From Protocol-specified Analyses

The changes from protocol-specified analyses are as following,

- In the statement regarding subjects who are not confirmed to be disease-free post-surgery or who withdraw prior to surgery, failure was changed from “a day after randomization” to “at randomization” for RFS, RRFS, LRFS and DMFS in [section 3.2](#).
- Safety endpoints related to talimogene laherparepvec DNA shedding and potential or known unintended exposure to talimogene laherparepvec were added as safety endpoints. The current protocol mentioned the analysis of these endpoints without specifically claiming them as safety endpoints.

---

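### RFS rule 4 censors a melanoma subject with a second malignancy the day after randomization, so later recurrence or death cannot count; LRFS, RRFS and DMFS have no such clause

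*SAP*

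**What the plan says.** SAP 4.1.1 defines the event broadly: "The event for RFS is defined as the first of local, regional, or distant recurrence of melanoma or death due to any cause". Protocol 10.1.1.1 has the same event, the "first of local, regional, or distant recurrence of melanoma or death due to any cause". Four rules follow in the SAP, and the fourth is "Subjects with a non-melanoma tumor or a second malignancy identified before or at surgery will be censored at the day after randomization".

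SAP 4.1.2.1.2 gives a narrower rule for the related endpoints. For LRFS and DMFS: "Subjects with a non-melanoma tumor identified at surgery will be censored at the day after randomization". For RRFS: "Subjects with a non-melanoma tumor identified at surgery will be censored a day after randomization". None of the three mentions a second malignancy or a finding made before surgery.

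The primary analysis uses the intent-to-treat set, and "All subjects will be analyzed according to their treatment randomization" (Protocol 10.1.2, repeated in SAP 7.1). The protocol's own special handling of RFS, in 10.2, deals with subjects who lack an R0 outcome or withdraw before surgery. It has no censoring rule for a second malignancy.

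**The concern.** Censoring a subject whose tumor turns out not to be melanoma can be defended, because melanoma recurrence is not a meaningful outcome for that person. The defence does not extend to a subject who has melanoma and, separately, another cancer. That subject can have a melanoma recurrence and can die, and the endpoint is defined to count both.

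Rule 4 removes all RFS follow-up on the strength of a finding that may arise weeks or months after randomization. If such subjects carry a higher risk, or are found more often in one arm, the primary estimate shifts. The primary endpoint can also miss a distant metastasis or death that a secondary endpoint in the same report counts.

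**Working it through.** **The rules side by side**

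| Endpoint | Trigger for censoring the day after randomization | When found |
|---|---|---|
| RFS | Non-melanoma tumor, or second malignancy | Before or at surgery |
| LRFS, RRFS, DMFS | Non-melanoma tumor | At surgery |

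Rule 4 lists the two triggers as alternatives, so a second malignancy is something other than a non-melanoma tumor. Take a melanoma subject with a second cancer found before surgery who later develops distant metastases or dies. For DMFS this is an event. For RFS the subject was censored at one day. Yet every DMFS event (distant metastasis or death) is an RFS event by definition.

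**Does any sensitivity analysis lift rule 4?** No. Sensitivity #1 is "regardless of surgical outcome, achieved by omitting rule 2". Numbers 2 and 3 change only which deaths count. The anti-cancer-therapy analyses in SAP 9.4.3 and the Efficacy Analysis Set leave rule 4 in place. Sensitivity #3 drops deaths unrelated to melanoma, which confirms that the primary analysis is meant to include them.

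**Is the rule declared?** SAP Section 11 opens with "The changes from protocol-specified analyses are as following" and lists two items: the timing of imputed failures and the added safety endpoints. Rule 4 is not there.

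**Can detection differ by arm?** Surgery falls in weeks 13 to 18 in Arm 1 and weeks 1 to 6 in Arm 2 (Protocol 6.3), a lag of 12 weeks at either end of the window. Arm 1 has protocol imaging at week 12 (Protocol 7.2.2, Table 2). Arm 2 has none between screening and surgery (Table 3). Detection could therefore be greater in Arm 1.

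**Two further gaps.** The word before has no start date, so a malignancy admitted under the exceptions to exclusion 203 could trigger the rule. A subject who withdraws before surgery after a second cancer is found meets both rule 3 (event at randomization) and rule 4 (censored), and no order of precedence is given.

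**The plan's figures first.** Inputs from SAP 3.2 and Protocol 3.5.1: 75 per arm, 2-year RFS 0.60 in Arm 2 and 0.70 in Arm 1, 10% drop-out, 18 months' accrual, 80% CI (z = 1.2816).

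- HR = ln 0.70 / ln 0.60 = 0.698 (SAP Table 1: 0.70).
- With 64 events, the 80% CI is 0.698 × exp(±1.2816 × 2/√64) = 0.507 to 0.962 (Table 1: 0.51 to 0.96).
- The probability that the CI lies below 1 is Φ(|ln 0.698| × √64/2 − 1.2816) = 0.562 (Table 1: 0.56).
- Expected events, with drop-out spread over 42 months, are 64.1 (Table 1: 64).

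Table 1 reproduces; it does not model rule 4.

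**Loss of precision, average-risk subjects.** Events remaining = 64 × (1 − q), where q is the assumed share of subjects censored by rule 4:

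| q | Subjects of 150 | Events left | Probability CI < 1 |
|---|---|---|---|
| 0 | 0 | 64 | 0.562 |
| 1% | 1.5 | 63.4 | 0.559 |
| 2% | 3 | 62.7 | 0.556 |
| 5% | 7.5 | 60.8 | 0.547 |
| 10% | 15 | 57.6 | 0.532 |

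**Bias from unequal detection.** Assume 3 second-malignancy subjects in each arm, of whom 3 in Arm 1 and 1 in Arm 2 are found before or at surgery (4% and 1.3% of 75). Simulated Cox estimates, 4,000 runs per row:

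| Hazard of affected subjects | HR, full follow-up | HR, rule 4 | Shift |
|---|---|---|---|
| Average | 0.694 | 0.693 | 0.001 |
| Double | 0.701 | 0.684 | 0.017 |
| Triple | 0.705 | 0.678 | 0.027 |

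The shift favours Arm 1, because more high-risk subjects are removed from that arm. A variant in which 3 versus 1 subjects are affected and all are found gives 0.715 to 0.698 at double hazard and 0.724 to 0.696 at triple, shifts of 0.017 and 0.028.

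**The case against.** The strongest reply is that this is a wording mismatch with little effect, and much of that stands.

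- A reader might infer that rule 4 breaks the intent-to-treat definition. It does not. That definition fixes who is in the set and in which arm, and a censored subject stays in both. What is lost is the follow-up, which is a matter of ITT principle only.
- A reader might infer that RFS times can exceed DMFS times. They cannot: an RFS time censored at one day is still the shorter. What fails is that every DMFS event should also be an RFS event.
- A reader might take differential censoring as established. The documents make it possible and no more. Exclusion 203 removes most other cancers of the past 3 years, and baseline imaging of chest, abdomen, pelvis and brain is required.
- The loss is confined to RFS. Under the wording of the other rules these subjects stay in LRFS, RRFS and DMFS, and their deaths count for OS.
- The primary analysis waits for the later of about 64 events or 2 years, so lost events need not lower the final count.

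A larger HR shift can be produced by assuming 6 versus 2 affected subjects at two to three times the hazard (0.728 to 0.694, and 0.742 to 0.686). That scenario places more high-risk subjects in Arm 1 to begin with, so it does not isolate the effect of unequal detection and should not be cited as the size of the problem.

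None of this explains why the primary endpoint should ignore recurrences and deaths that it is defined to count.

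**Conclusion.** Wrong as written, low impact. The textual conflict is certain: rule 4 stops counting events that fall within the RFS definition, for subjects whom the three related endpoints keep. The starting point for the removal is the day after randomization, which is not the SAP's Study Day 1 (first dose or surgery).

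The size rests wholly on assumption, because the documents give no count. With 3 versus 1 subjects censored and up to triple hazard, the HR moves by about 0.03 or less in favour of Arm 1. That is small beside the planned 80% CI of 0.51 to 0.96, in a trial with no formal test. The case for changing the rule is coherence of the primary endpoint, not a demonstrated bias.

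**What to change.** In SAP 4.1.1, delete the second-malignancy clause and limit rule 4 to subjects whose tumor proves on histology not to be melanoma. Use the same wording, including when the finding must be made, for RFS, LRFS, RRFS and DMFS. For subjects with melanoma and a second malignancy, count recurrence or death as for anyone else.

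State which rule prevails when rule 4 and rule 2 or 3 both apply. Add one RFS sensitivity analysis without rule 4, since even the narrowed rule acts on a finding made after randomization. List the rule in SAP Section 11.

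No new data are needed, because Protocol 7.2.4 already follows all randomized subjects. The cost is SAP wording, minor programming, and a change to the primary endpoint rules in an open-label trial whose study team conducts an RFS interim about 1 year after the end of randomization. The change should therefore be dated and documented before the RFS analyses.
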